3.4 Candidate Computable Phenotype Criteria (at selected US sites only)

1. Recent diagnosis codes including oligo-articular JIA as well as undifferentiated/unspecified JIA types only, AND
2. Participants age ≥ 2 years old and ≤ 16.5 years old, AND
3. Seen in pediatric rheumatology clinic with first inclusion criteria diagnosis code within the preceding 20 weeks OR scheduled for upcoming pediatric rheumatology clinic visit with prior diagnosis of any type of arthritis within the preceding 20 weeks, AND
4. None of the following prior medications: systemic glucocorticoids, DMARDs OR biologics, AND
5. No prior diagnosis codes for Inflammatory Bowel Disease (IBD), systemic-onset JIA, sacroiliitis or ankylosing spondylitis, psoriasis, or uveitis

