1 INTRODUCTION

Juvenile idiopathic arthritis (JIA) is a heterogeneous, incompletely understood collection of inflammatory arthritides of unknown etiology defined by age at onset prior to 16 years.¹ With a prevalence of approximately 1 per 1,000 children, and many clinical phenotypes, JIA is one of the most common chronic diseases of childhood. JIA often persists into adulthood causing significant morbidity and impairing quality-of-life.²⁻¹⁶ More than 50% of children with JIA present with “limited” disease, defined as arthritis involving ≤ 4 cumulative joints and no uveitis.¹⁷ Children with limited JIA may meet criteria for one of 4 separate categories of JIA defined by the International League of Associations for Rheumatology (ILAR): oligoarthritis, enthesitis-related arthritis, psoriatic arthritis, and undifferentiated arthritis.¹ However, scant evidence supports differential treatment of children based upon ILAR categories, which are fraught with uncertainties and inconsistencies.¹⁸⁻²⁷ Basing treatment decisions upon the number of joints affected to date, in contrast to ILAR categories, was endorsed by the 2011 American College of Rheumatology (ACR) Recommendations for the Treatment of JIA and more closely reflects current clinical practice.^{28, 29} Therefore, the Limit-JIA study focuses on all children presenting with arthritis of ≤ 4 joints without uveitis. For the purpose of this trial, this phenotype is termed “limited JIA”. Irrespective of ILAR category, children with limited JIA may develop significant morbidity, with only a minority achieving clinically inactive disease 12-18 months after disease onset.^{4, 8, 30-32}

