Disease extension in limited JIA. Children initially presenting with limited JIA frequently experience disease, defined as the development of polyarthritis (≥ 5 joints) or anterior uveitis. Both polyarthritis and uveitis are associated with worse clinical outcomes, including increased long-term physical disability and disease activity levels compared to children who present with polyarthritis at the time of diagnosis.^{2, 6, 33-42} Fifty percent or more of children with limited JIA develop extension of oligoarthritis to polyarthritis (defined as ≥ 5 joints), including more than 25% within 2 years of disease onset.^{2, 30, 39, 43-45} Reported arthritis extension rates vary between studies, likely reflecting genetic and environmental variation and methodological differences in the inclusion and follow-up of study participants.⁴⁶ Of note, previous studies focused on the ILAR category of oligoarthritis and did not include enthesitis-related arthritis or psoriatic arthritis, which have considerably higher rates of arthritis extension.⁴³

One factor likely contributing to disappointing clinical outcomes for children presenting with early, limited JIA is delayed initiation of effective disease modifying anti-rheumatic drugs (DMARDs) and/or biologics.^{35, 47} The development of anterior uveitis is also an important manifestation of limited JIA and can lead to permanent ocular disabilities such as glaucoma, cataracts, and vision loss.³⁶⁻³⁸ Approximately 20% of children with limited JIA develop anterior uveitis, most often within 2 years of arthritis onset.^{2, 30, 48} The development and subsequent severity of uveitis are often independent of arthritis manifestations, i.e., children may develop uveitis without concomitant extension to polyarthritis and vice-versa.⁴⁹ Lastly, a number of children may have persistent, limited JIA but inadequate response to treatment with nonsteroidal anti-inflammatory drugs (NSAIDS) and intra-articular glucocorticoid injections, requiring ongoing systemic treatment with DMARDs or biologic agents, even without extension of arthritis or development of new uveitis.⁵⁰⁻⁵² We therefore seek to determine whether early treatment with a 24-week course of abatacept (Orencia) will delay, diminish, or prevent the important outcomes of polyarthritis or uveitis, or need for systemic DMARD or biologic use during the study period and longer-term follow-up in the Childhood Arthritis and Rheumatology Research Alliance (CARRA) Registry.

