3.2 Clinical Trial Inclusion Criteria

To be eligible for this trial, participants must meet all of the following criteria in order to be included in the study:

1. Age \geq 2 years old and \leq 16.5 years old
2. Clinical diagnosis of JIA by a pediatric rheumatologist within the past 6 months
3. Arthritis affecting \leq 4 joints between disease onset and enrollment
4. Enrollment in the CARRA Registry
5. Participants of childbearing potential must agree to remain abstinent or agree to use an effective and medically acceptable form of birth control from the time of written or verbal assent to at least 66 days after taking the last dose of study drug.
6. Weight \geq 50 kg (Canadian Sites only)

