8.2.2 Enhanced Study Recruitment (US Based Sites Only)

The outcome for screening efficacy using enhanced study recruitment will be assessed as the marginal difference for successful identification of study participants who meet the limited JIA inclusion criteria. We will compare absolute and relative numbers of eligible participants identified by computable phenotype augmented screening lists vs screening lists generated by current, ad-hoc processes alone. In addition, the efficiency of augmented screening will be assessed as the number of additional records requiring manual screening and chart review in order to identify one additional eligible participant.

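### The candidate EHR phenotype (3.4 item 1) queries only oligoarticular and undifferentiated/unspecified JIA codes, although the trial also enrolls enthesitis-related arthritis and psoriatic arthritis without psoriasis

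*Combined protocol and SAP*

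**What the plan says.** Section 3.4 lists five criteria for the EHR query, each joined to the next by AND. Item 1 reads "Recent diagnosis codes including oligo-articular JIA as well as undifferentiated/unspecified JIA types only, AND". Item 3 has two branches. The second takes in a child "scheduled for upcoming pediatric rheumatology clinic visit with prior diagnosis of any type of arthritis within the preceding 20 weeks". Item 4 requires "None of the following prior medications: systemic glucocorticoids, DMARDs OR biologics, AND". Item 5 removes children with codes for inflammatory bowel disease, systemic JIA, sacroiliitis or ankylosing spondylitis, psoriasis, or uveitis.

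The trial population is wider. The Introduction says that children with limited JIA may fall under "oligoarthritis, enthesitis-related arthritis, psoriatic arthritis, and undifferentiated arthritis", and that "the Limit-JIA study focuses on all children presenting with arthritis of" four or fewer joints without uveitis. Inclusion criterion 2 in section 3.2 asks only for "Clinical diagnosis of JIA by a pediatric rheumatologist within the past 6 months". Table 3 (4.3.3) has a row for enthesitis-related arthritis, and its footnote counts psoriatic arthritis without current or past psoriasis in the oligoarthritis rows. Section 9.4.1 plans subgroup comparisons for both categories.

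The screening outcome in 8.2.2 is the marginal difference in "successful identification of study participants who meet the limited JIA inclusion criteria", comparing phenotype-augmented lists with lists from existing ad hoc processes.

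**The concern.** The Introduction justifies EHR screening by more timely and more representative enrollment and by less ascertainment bias. A code list that leaves out two of the four categories works against that aim. Children who carry only an omitted code cannot count as added yield in 8.2.2, although they meet the inclusion criteria that the outcome is defined on.

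There is also a possible route to the primary comparison. The Introduction notes that earlier studies "did not include enthesitis-related arthritis or psoriatic arthritis, which have considerably higher rates of arthritis extension". If list-based enrollment lowers the share of these categories in Part II, the untreated risk of the abatacept group may differ from that of the 428 Registry controls. The primary logistic model in 9.2 contains only the treatment term and would not adjust for it.

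**Working it through.** **1. The query as logic.** A child is listed only if items 1, 2, 3, 4 and 5 are all true. For a child whose only JIA code is enthesitis-related or psoriatic arthritis, item 1 is false. The any-arthritis branch of item 3 cannot restore that child, because it is joined to item 1 by AND. Items 1 and 3 therefore fit together poorly: for a child with an omitted code, the wider branch has no effect.

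**2. Who is affected.** The exclusions in 3.3 for psoriasis and sacroiliitis already remove part of both categories, so the missed group is the remainder. A child first coded as unspecified JIA passes item 1 and can still be listed.

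**3. Yield.** The documents give no ILAR shares and no phenotype sensitivity. If a share *s* of eligible children carry only an omitted code, sensitivity is at most 1 − *s*. On an assumed range of 10% to 30%, the ceiling is 90% to 70%.

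**4. Relative share among enrollees.** Suppose the categories are a share *s* of conventional enrollment and the lists add a fraction *g* of extra enrollees, none from these categories. The new share is *s*/(1 + *g*).
- *s* = 10%: *g* = 10% gives 0.10/1.1 = 9.1%; *g* = 100% gives 0.10/2 = 5.0%.
- *s* = 30%: 0.30/1.1 = 27.3%; 0.30/2 = 15.0%.

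The number of such children does not fall; only their proportion does. All values of *s* and *g* are assumptions.

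**5. Primary comparison.** The plan's own figure comes first. With 80 versus 428 patients, 15% versus 34.3%, one-sided 0.025 and the Wald test in the treatment-only logistic model, exact enumeration gives power 0.958 against 0.956 in Table 7. With equal case mix the same test has one-sided type I error 0.022.

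Now let the categories be a share *s* of the controls with a composite rate *r* times that of the others, and let their share in the trial be *s*′ = *s*(1 − *f*). Then:
- rate in the others: *b* = 0.343/(1 − *s* + *s r*)
- expected untreated rate in the trial: *p* = *b*(1 − *s*′ + *s*′*r*)

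Two cases with *s* = 0.20 and *f* = 0.5, so *s*′ = 0.10:
- *r* = 1.5: *b* = 0.343/1.10 = 0.312; *p* = 0.312 × 1.05 = 32.7%, below 34.3%. Type I error is 0.040.
- *r* = 0.8: *b* = 0.343/0.96 = 0.357; *p* = 0.357 × 0.98 = 35.0%, above 34.3%. The shift now works against abatacept.

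Across *s* = 10% to 30%, *r* = 1.25 to 2 and *f* = 25% to 50%, *p* runs from 34.1% down to 30.3% and type I error from 0.024 to 0.092. If the conventional share equals the control share, step 4 gives 1 − *f* = 1/(1 + *g*). So *f* = 50% needs *g* = 100%: half of all Part II enrollees would have to come from the lists, with none in the omitted categories. No input to this step except 0.343, 80, 428 and 0.025 is in the documents. The sign depends on *r*, which they do not give.

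**6. Item 4 against the other glucocorticoid rules.** Item 4 bars any prior systemic glucocorticoid. Exclusion 7 in 3.3 looks back 30 days and allows a short oral prednisone course. The active joint count entry in 4.3.2 says a patient treated with systemic medication is no longer eligible, and the synopsis and 2.1 count glucocorticoids among systemic medications. Section 6.6 allows a short course before enrollment under stated COVID-19 conditions. Section 4.5 makes starting systemic glucocorticoids between screening and enrollment a screen failure. These texts do not agree with one another.

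**The case against.** The strongest reply is that 3.4 is headed as a candidate definition. Section 4.10 refines the queries themselves against a list of children known to have limited JIA, found by other means, and limited JIA spans all four categories. Missed enthesitis-related or psoriatic cases on that list would appear as false negatives and prompt wider codes. This largely stands: it would be wrong to infer that EHR screening can never find these children. But 4.10 does not require the positives to cover each category, and methods for finding them vary by site, so detection of the gap is likely rather than assured.

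Second, the lists are used at a subset of US sites (4.1) and are added to conventional screening (2.2.2). That stands. A reader might infer that recruitment is steered away from these categories; the documents support a possible fall in relative share, not removal.

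Third, a narrow query can only lower the augmented yield, which works against the EHR hypothesis in 2.2.2, and 4.10 accepts a trade of sensitivity against specificity. That also stands: the 8.2.2 comparison is not invalidated. But nothing says that this omission is the intended trade.

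Fourth, a reader might infer a bias in favor of abatacept. The Introduction supports higher arthritis extension only, without a rate. The endpoint in 8.1 also includes uveitis and systemic medication. Table 3 gives enthesitis-related arthritis eye exams only at screening and month 12, its least frequent schedule. Section 9.1 says the controls met major eligibility criteria, and their ILAR mix is not in the text available. The inference is not established.

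**Conclusion.** The mismatch between 3.4 item 1 and the trial population stands on the text alone and needs no assumption. As written, the list omits eligible children who carry only an enthesitis-related or psoriatic arthritis code. This lowers the 8.2.2 yield and may lower these categories' relative share among EHR-sourced enrollees. The size is unknown; the 90% to 70% sensitivity ceiling and the share figures are illustrations on assumed inputs.

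An effect on the primary comparison is possible because 9.2 has no case-mix adjustment, but neither its direction for the composite nor its size can be determined. The type I error range above shows sensitivity to assumptions and is not an estimate for this trial. The point is a cheap improvement, not a threat to the trial's validity.

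**What to change.** - In 3.4 item 1, add the enthesitis-related and psoriatic arthritis codes. Keep the item 5 exclusions, and check that the psoriasis code set there does not also catch the psoriatic arthritis codes just added. This brings item 1 into line with the any-arthritis branch of item 3. If the omission is deliberate, say so, give the reason and reword item 3.
- In 4.10, require the gold-standard positives to cover all four ILAR categories.
- In 8.2.2, report phenotype sensitivity by ILAR category and the ILAR mix of enrollees by screening route. Set that mix beside the mix in the 428 controls, so that any case-mix difference is visible when the primary result is read.
- Reconcile item 4 with exclusion 7 in 3.3 and with 4.3.2, 4.5 and 6.6, so that the query follows whichever glucocorticoid rule the sponsor confirms.

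The cost is a revised query and more records for manual review at EHR sites, which may raise the 8.2.2 count of records reviewed per additional eligible child. Adding the codes changes neither eligibility nor visits.

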3.5 Ethnography Criteria (at selected US sites only)

There are four research study participant populations:

1. Families who are asked to participate in the clinical trial (Limit-JIA)
 - a. Inclusion: Parents/guardians of JIA participants ≥ 2 years old and ≤ 16.5 years of age at the time of diagnosis, who were asked to participate in Limit-JIA, regardless of decision to enroll or not in the Limit-JIA study
 - b. Exclusion: Non-English speakers
2. Site primary investigators
 - a. Inclusion: Primary site investigator for Limit-JIA
 - b. Exclusion: Non –English Speakers

3. Study coordinators
 - a. Inclusion: Coordinators participating in the Limit JIA trial
 - b. Exclusion: Non-English Speakers
4. Clinicians
 - a. Inclusion: Pediatric rheumatology providers e.g. Medical Doctors (MDs, DOs) and Nurse Practitioners (NPs) at participating sites who are recruiting for the Limit-JIA trial but are not the study coordinator or site primary investigator.
 - b. Exclusion: Non-English Speakers

4 STUDY DESIGN

4.1 Overview of Study

The study treatment consists of an open label 24-dose course of weekly subcutaneous (SQ) abatacept (Orencia) plus usual care, versus usual care subject comparators from the CARRA Registry to prevent the development of polyarthritis or uveitis, or initiation of systemic glucocorticoid, DMARD, and/or biologic medication within 12 months of enrollment in children with recent-onset limited JIA. Patients enrolled in the CARRA Registry receiving usual care who meet Limit-JIA inclusion/exclusion criteria will constitute the comparator arm, providing the proportion of children that develop disease extension on usual care alone.

There are 6 study visits: screening, enrollment, approximately month 3 (M3 visit), month 6 (M6 visit), month 9 (M9 visit), and month 12 (M12 visit [end of study]). The screening visit may be combined with the enrollment visit if all procedures can be completed and participant qualifies for the study. Clinical trial visits may occur either in person or via telehealth except for the screening or enrollment visits. One of these visits must be conducted in the clinic. The month 12 end of study visit must also be conducted in the clinic.

In order to enhance study recruitment and timely enrollment, a subset of Limit-JIA US based clinical trial sites will incorporate enhanced cohort identification of potential study participants that incorporates EHR-based algorithms to predict the presence of limited JIA. Specifically, a ‘computable phenotype’ will be utilized to generate screening lists of potentially eligible, recently diagnosed limited JIA patients who may be considered for enrollment. These EHR-based screening lists will then be further reviewed by site staff for study eligibility.

Study participant identification and enrollment using enhanced screening will be compared to use of traditional screening methods alone at this subset of sites. In addition, at a subset of US based sites, all enrolled CARRA Registry participants with JIA will have registry data supplemented by selected EHR data elements, which will be linked by the site and made available in the CARRA Data Warehouse, enabling analyses of registry data completeness.

In order to gain a better understanding of barriers to recruitment, enrollment and retention, a subset of participating US based clinical trial sites will participate in a sub-study focused on the patient journey through the clinical trial. This sub-study will follow a quasi-experimental time-series cross-sectional study design with initial tools development followed by three rounds of alternating data collection and iterative tools development to identify barriers and develop improved resources and processes to improve trial recruitment and retention of study participants.

4.2 Treatment Arms

Limit-JIA is a prospective open-label clinical trial. Children diagnosed with limited JIA (≤ 4 active joints and no uveitis) in the previous 6 months will be treated with a 24-dose course of weekly SQ abatacept (Orencia) plus usual care that may include NSAIDs and/or intra-articular glucocorticoids followed by 6 months of usual care. Abatacept (Orencia) will be dosed using the weight-based SQ pediatric dosing provided in the package insert (Table 1 below).

Table 1: Study drug dosing

Study drug dose will be adjusted for weight changes during the duration of the study drug administration period.

Study Drug	Dose by Weight	Dosage Form	Route	Dosage Frequency	Administration
abatacept (Orencia)	10 kg to < 25 kg: 50 mg	Solution for injection in pre-filled syringe (50mg in 0.4mL)	SQ	Once weekly	US based clinical sites only
abatacept (Orencia)	\geq 25 kg to < 50 kg: 87.5 mg	Solution for injection in pre-filled syringe (87.5mg in 0.7mL)	SQ	Once weekly	US based clinical sites only
abatacept (Orencia)	\geq 50 kg: 125 mg	Solution for injection in pre-filled syringe (125mg in 1mL)	SQ	Once weekly	US and Canadian based clinical sites

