Study Design	Prospective, open-label clinical trial. with stratified enrollment of participants based upon baseline risk of developing polyarthritis or uveitis
Treatment Regimen	
 • Abatacept (Orencia) plus usual care for 24 weekly doses with ongoing usual care and 24 weeks of follow up for a total of 48 weeks. • Usual care for 12 months (48 weeks) as recorded in the CARRA Registry • Usual care is defined as NSAIDs and/or intra-articular glucocorticoids at the discretion of the treating provider
Duration of Study Participation	12 months (48 weeks)
End -of Study- Definition	Date of last study participant's last visit
Number of Study Participants	89
Number of Sites	Up to 30

Primary Endpoint	Proportion of participants with disease extension (development of polyarthritis or uveitis) or need for systemic medication (s) for JIA (i.e. one or more of the following: systemic glucocorticoids, DMARD or biologic) within 12 months post-enrollment.
Secondary Endpoints	
 • PRO group differences including PROMIS® measures (pain interference, fatigue, upper extremity function, mobility, anxiety, depression, and global health) and medication side effects (JAMAR), CHAQ • Proportion of children achieving clinical inactive disease and/or remission • Number of new joints with arthritis • Cumulative number of glucocorticoid joint injections • Serious adverse events • Juvenile arthritis disease activity scores (JADAS) • Elapsed time from enrollment to disease extension, uveitis or systemic DMARD medication use • Proportion of participants with disease extension (development of polyarthritis or uveitis)
Study Schedule Definitions	
 • 6 months is equal to 24 weeks or 24 doses of abatacept • 12 months is equal to 48 weeks

INVESTIGATOR STATEMENT

I have read the protocol, including all appendices and the investigator brochure, and I agree that it contains all necessary details for me and my staff to conduct this study as described. I will personally oversee the conduct of this study as outlined herein and will make all reasonable efforts to complete the study within the time designated.

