Rationale for costimulatory blockage treatment for JIA. Abatacept (Orencia) is an approved, standard of care treatment for adults with rheumatoid arthritis (RA; USA and Canada) and for children with

polyarticular JIA (USA [SQ and IV] and Canada [IV form only]). Abatacept (Orencia) selectively inhibits a costimulatory signal required for T-cell activation, which is hypothesized to be an early step in the development of inflammatory arthritis. The 50 mg, 87.5 mg and 125 mg, SQ doses are approved for use in pediatric patients in the United States, whereas the 125 mg SQ dose is the only form approved for use in Canada.

Clinical trials in adults with RA have established that early treatment with biologic agents and DMARDs, during a “window of opportunity,” improves long-term outcomes and reduces future disability.⁵⁴⁻⁵⁶ In particular, a randomized, double-blind trial in undifferentiated arthritis (very early RA) demonstrated that a 6-month course of abatacept (Orencia) delayed disease progression in the majority of participants.⁵⁷ Unpublished results from a recent study presented at the 2021 American College of Rheumatology Annual Meeting showed that a 6 month course of abatacept reversed subclinical arthritis in participants at high risk for RA.^{57, 58, 67} While such data is currently limited to adult RA and not JIA, the results strongly support the study of abatacept (Orencia) as a preventative agent for extension of disease in limited JIA.

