³ Baseline Ophthalmology exam may occur at any time between the screening visit and the enrollment visit, including on the day of the screening visit or the enrollment visit. Prior baseline exam will be accepted if done within 45 days of enrollment.

⁴ Only if obtained as SOC. Not required specifically for study.

⁵ Screening CBC and CMP must be obtained within 2 months prior to enrollment. If not available or abnormal from previous SOC labs, CBC and CMP must be obtained prior to enrollment.

⁶ ANA results required prior to enrollment.

⁷ See Table 5 for specific instructions.

⁸ For females with childbearing potential and should be repeated at any time during study duration per standard of care by participant's provider.

⁹ Subjects who have not been screened for Hepatitis B as part of SOC will get one as part of screening or enrollment. Study drug can be dispensed prior to obtaining study results. Patient families will be instructed to not administer drug until a negative result is confirmed. If test results are positive, the subject will be discontinued from the study.

¹⁰ Enrollment may occur during screening visits or at a separate specific enrollment visit.

¹¹ Subjects who did not have a Quantiferon Gold or TB test as part of SOC will get one as part of screening or enrollment. Study drug cannot be administered in the absence of a negative test result.

¹² A 3- or 6-month supply of abatacept will be provided at the enrollment visit. Re-supply will occur at M3 if a 3-month supply was provided at enrollment.

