12. CHAQ
13. Juvenile Arthritis Multidimensional Assessment Report (JAMAR)
14. Juvenile Arthritis Disease Activity Score (JADAS)
15. Drug Dispensation (a 3 month or a 6 month supply can be provided)
16. Dose Instructions/Administration
17. Ophthalmology Exam (if not available at screening)

4.8 Post Enrollment Procedures (Month 3 to Month 12; in person or via telehealth) Month 3/Month 6 (+/- 2 weeks; in person or via telehealth)

1. Physical examination
2. Joint Exam - Active joint count
3. Interval history to include interval use of NSAIDs and intra-articular glucocorticoid injections, new co-morbid conditions (including psoriasis), encounters with health care professionals (specifically in response to uveitis, active arthritis, or serious adverse events).
4. Drug dispensation (Month 3 only – re-supply, only if a 3 month supply was provided at Baseline)
5. Drug adherence
6. Ophthalmology exam per Table 3
7. Concomitant Medications
8. Physician Global Assessment
9. Parent Global Assessment
10. Selected PROMIS® measures – See Table 5
11. CHAQ (6 month only)

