6.1 Abatacept (Orencia) – Study Drug

Participants enrolled to receive SQ abatacept (Orencia) will receive training and study materials (3 month or 6 month drug supply) on the day of enrollment. The first dose should be administered at the site or at home with telehealth guidance from the investigator or other study staff once all test results have been verified. All study participants enrolled will be trained by the study staff on study drug administration. A resupply of IP will occur at the three-month visit if a 6-month supply was not provided at enrollment.

The 50 mg, 87.5 mg and 125 mg SQ doses that are approved for use in pediatric patients in the United States will be supplied by a US-based depot. The 125 mg SQ dose approved for use in Canada will be sourced from a Canadian vendor.

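### The rule that dose follows weight has no scheduled point at which to act when a 6-month supply is dispensed at enrollment

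*Combined protocol and SAP*

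**What the plan says.** Section 4.2 sets the dosing rule above Table 1: "Study drug dose will be adjusted for weight changes during the duration of the study drug administration period". Table 1 has three bands (10 to under 25 kg, 25 to under 50 kg, and 50 kg or more), each with its own prefilled syringe of 50, 87.5 or 125 mg. The two lower strengths are marked for US sites only.

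Dispensing is covered in several places. Table 2 footnote 12 says: "A 3- or 6-month supply of abatacept will be provided at the enrollment visit", and then: "Re-supply will occur at M3 if a 3-month supply was provided at enrollment". The Month 3/Month 6 list in Section 4.8 allows dispensing at Month 3 alone, as a resupply, and "only if a 3 month supply was provided at Baseline". Section 6.1 says: "A resupply of IP will occur at the three-month visit if a 6-month supply was not provided at enrollment". The synopsis fixes the length of the course: "6 months is equal to 24 weeks or 24 doses of abatacept".

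On visit format, Section 4.1 says: "Clinical trial visits may occur either in person or via telehealth except for the screening or enrollment visits". It later adds that the Month 12 visit must be in clinic. Section 4.3.2 describes the physical examination as covering organ systems and vital signs with temperature; it does not name weight. On Canada, the Introduction describes the strengths approved in the United States, "whereas the 125 mg SQ dose is the only form approved for use in Canada".

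**The concern.** Section 4.2 is written as a requirement, and with fixed-strength syringes it can be met only by supplying a different syringe. If all 24 syringes are handed over on the enrollment weight and no later dispensing is scheduled, a site that follows the dispensing text cannot also follow the dosing text for a child who changes band. The two instructions then conflict on a route that the protocol expressly allows.

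What is at stake is fidelity to the regimen that the trial sets out to evaluate. Whether a growing child near 25 or 50 kg receives the Table 1 strength could depend on which supply option the site chose. With no weight named after enrollment, a departure could also go unrecorded.

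**Working it through.** The plan states no figure on this point, so the check is a side-by-side reading with some dispensing arithmetic. The only plan figure used is the enrollment target in Section 9.4.2, which reproduces: 80 / (1 − 0.10) = 88.9, rounded up to 89.

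**Step 1: where can the rule act?** The course is 24 weekly doses.

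| Supply at enrollment | Doses chosen on enrollment weight | Doses dispensed later | Scheduled points for a change of strength |
|---|---|---|---|
| 6-month | 24 | 24 − 24 = 0 | none |
| 3-month | 12 | 24 − 12 = 12 | one, at Month 3 (week 12 ± 2) |

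On the 3-month route, a child who crosses a band before Month 3 waits at most about 10 to 14 weeks. A child who crosses after Month 3 already holds the remaining syringes. Interim visits do not fill the gap: Table 2 ties them to symptoms or serious adverse events, and the interim list in Section 4.8 has no dispensing item.

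**Step 2: is there a weight to act on?** Month 3 includes a physical examination with vital signs, so weight may be taken in practice. It is not named, Month 3 may be by telehealth, and nothing says how a weight is then obtained.

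**Step 3: how far apart are adjacent strengths?**
- At 25 kg: 50 / 87.5 = 0.57, so the lower strength is 43% below the next.
- At 50 kg: 87.5 / 125 = 0.70, or 30% below.
- For a fall below 50 kg: 125 / 87.5 = 1.43, or 43% above.

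**Step 4: Canada.** Entry there requires at least 50 kg, so nobody can cross a band upward. A participant who fell below 50 kg would move to a band whose syringe Table 1 restricts to US sites.

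**Step 5: how many children?** The documents give no weight distribution, growth rate or split between supply routes, so all of these are assumptions. With weights spread evenly over a range of width W and a gain of g kg during the course, the share crossing one of the two cuts is 2g/W.

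| W (assumed) | g = 1 kg | g = 3 kg |
|---|---|---|
| 50 kg | 2/50 = 4%; 0.04 × 89 = 3.6 | 6/50 = 12%; 0.12 × 89 = 10.7 |
| 60 kg (10 to 70 kg) | 2/60 = 3.3%; 3.0 children | 6/60 = 10%; 8.9 children |

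These counts are of children who cross a cut at any time. Multiplying by the share on a 6-month supply, which may lie anywhere from 0 to 1, gives 0 to about 11 of 89 on that route. If gain is steady, crossings spread evenly over the 24 weeks, so a child who crosses has on average about 12 of the 24 doses still to come.

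**The case against.** A reader might infer that the adjustment rule cannot be carried out at all, or that children who cross a band do stay on the earlier strength. The documents support neither. On the 3-month route, Month 3 has both an examination and a dispensing step, so the rule can act there. No passage says a child keeps the earlier strength; Section 4.2 says the reverse. Nothing expressly forbids an unscheduled exchange, and Section 11.4 already requires records of returned drug.

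Several supporting points are also weaker than they look:
- Footnote 12 and Section 6.1 say when resupply will happen; they do not exclude other resupply. Only Section 4.8 uses limiting words.
- Table 2 marks dose and instructions at enrollment only, but this fits the training described in Section 6.1 and does not show that dose assignment ends there.
- Weight has no row in Table 2 even at screening and enrollment, where eligibility and the first dose depend on it. The table plainly does not list every measurement.
- Telehealth at Month 3 is allowed, not required.
- The Canadian case needs weight loss across 50 kg within 24 weeks.
- The step between strengths overstates the difference per kilogram: 50 mg at 28 kg is 50/28 = 1.79 mg/kg, while Table 1 itself gives about 87.5/50 = 1.75 mg/kg just under 50 kg.

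All of this stands, and it limits the reach and likely effect of the point. It does not remove the conflict on the 6-month route, where Section 4.8 allows no later dispensing and no exchange is described. Relying on unwritten exchanges leaves each site to improvise.

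**Conclusion.** The point holds in a bounded form. On the 6-month route, the mandatory adjustment rule in Section 4.2 and the dispensing limit in Section 4.8 cannot both be followed for a child who changes weight band. Under the schedule as written, that child would receive a strength other than the Table 1 strength for the remaining doses. On the 3-month route the rule can act once, and the plan does not say how weight is obtained if Month 3 is remote. The Canadian limb is real but narrow.

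The number on the 6-month route is 0 to about 11 of 89. This rests on an assumed gain of 1 to 3 kg, weights spread evenly over 50 to 60 kg, and the unstated supply split; the upper end also makes no allowance for Canadian participants, who cannot cross upward.

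A reader might go on to infer a stated dilution of the treatment effect. The documents give no dose-response information, so none can be calculated, and the plan's sample size and power figures are not in question. The reason to act is that the instructions conflict and that departures could go unseen.

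**What to change.** Reconcile Section 4.2 and Table 1 with Table 2 (including footnote 12), Section 4.3.2, Section 4.8 and Section 6.1, so that the dosing rule and the dispensing schedule agree in three situations: a 6-month supply at enrollment, a telehealth Month 3 visit, and Canadian sites with a single strength. If the adjustment rule is kept, name weight as a Month 3 assessment and say how it is obtained remotely. If the rule is not meant to apply after enrollment, Section 4.2 should say so. Which rule applies is for the sponsor to decide; no dose or re-dispensing rule is proposed here.

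The cost is protocol wording and, if the rule is kept, one weight entry per child and possibly some replacement supply. The downside is that some syringes already dispensed may be wasted.
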